All innovation in medicine needs to be justified in terms of cost-benefit. We decided to use stafftime as the primary outcome of the current study. It is estimated that the time of the SR procedure is equal to the time presently used in the SC procedures. Use of the self-applied polysomnography together with machine-learning algorithms of sleep analysis and the digital platform of patient symptom self-reporting will reduce staff time on one hand. On the other hand, user instructions to the patient for the different technologies as well as the evaluation of new information may consume more time compared with the current procedure. We decided to use a non-inferiority study design with 30 minutes as a threshold for equality of staff time within the setting of 24 sleep centers in Europe.

Calculation of the power sample is based on a previous publication (Fischer 2008) and the following assumptions determined from a Delphi round (expert consensus) amongst the participating study centers. More detailed information on staff time for PSG and HSAT currently used at 24 different study sites are not available in the literature. One pilot study for the SR pathway has been performed but no detailed measurement of staff time was performed. However, realistic estimates can be made (see table below).

Work modules	Standard PSG	Standard HSAT	Sleep Revolution	Value
Preparation technical pre/post	15	10	35	
Instructions/Hook up	20-40	5-20	5-30	
Performance of the sleep test	120-480	0 (patient)	0 (patient)	
Evaluation of the sleep test	30-120	5-30	30-90	
Questionnaires	5	5	10	
Additional equipment	0	0	15	
Doctor: interpretation, communication	30-60	15-30	45-60	
Staff time: Estimated range of the mean	220-720	40-95	140-240	
Staff time: Estimated standard deviation of the mean	180	30	60	120

Power calculation:

Significance level (alpha)	1%		
Power (1-beta)	90%	You could say:	
Standard deviation of outcome	120	between the standard and experimental treatment, then 834	
Non-inferiority limit, d	30	sure that the lower limit of a one- sided 99% confidence interval (or equivalently a 98% two-sided	
Sample size required per group	417	confidence interval) will be above the non-inferiority limit of -30.	
Total sample size required	834		
Technical note		Reference	
Calculation based on the formula:		Julious SA. Sample sizes for clinical trials with Normal data. Statis Med. 2004; 23:1921-1986.	

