8.4. Primary Analysis

Primary outcome: Staff time– comparison between standard care and the Sleep Revolution model in patients with suspected obstructive sleep apnea (OSA).

• Primary Outcome

The primary outcome is staff time, spent for the sleep apnea diagnostic pathway (V1a to V1 c) measured in minutes, required per patient, for the randomized study procedure (SC or SR care).

• Study Design

This is a parallel-group design comparing two patient groups (Group A and Group B). Patients are nested within centers, and the analysis will account for potential clustering by center. This is a non-inferiority comparison in staff time.

• Analysis Population

The primary analysis will be conducted on the intention-to-treat (ITT) population, including all randomized patients according to their assigned group.

• Descriptive Statistics

Descriptive statistics will be presented for staff time by group, including:

- Mean (standard deviation), Median (interquartile range), and Minimum/Maximum

• Primary Analysis

To compare staff time between the two groups while adjusting for center effects, a linear mixedeffects model (LMM) will be used:

- Fixed effect: Group (Group A vs. Group B)
- Random effect: Center (to account for clustering)
- Model specification:

StaffTime_{ij} = $\beta_0 + \beta_1 * Group_{ij} + u_j + \varepsilon_{ij}$

where:

- StaffTime_{ij} is the staff time for patient i in center j
- β_0 is the intercept
- β_1 is the fixed effect of group
- u_j ~ N(0, σ_u^2) is the random effect for center
- $\varepsilon_{ij} \sim N(0, \sigma^2)$ is the residual error

Adjustment for potential confounders would be considered if groups are unbalanced for some covariate due to random.

• Estimates and Inference

The estimated mean difference in staff time between groups will be reported with 95% confidence intervals and p-values.

Model assumptions (normality of residuals, homoscedasticity) will be checked using diagnostic plots.

Sensitivity Analyses

A per-protocol analysis will be conducted to assess robustness.

If the distribution of staff time is highly skewed, a log-transformation or non-parametric methods may be considered.

Two additional sensitivity analyses will be performed based on patient characteristics like A) sex and B) by the median of the age (total patient population).

Further sensitivity analysis will be performed regarding subgroups of centers and patient characteristics for sleep test methodology in the standard care arm:

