The statistical programs SPSS and the R software package R version 4.3.1, located in a data cluster at Reykjavik University, Iceland, are available. All analysis will be performed by authorized personnel on this cluster.

• Data Management Software: REDCap and Excel are used for data management.

13. Reporting and Interpretation of Results

• Presentation of Results:

Results will be clearly presented using tables, figures, and confidence intervals: **Tables** will summarize descriptive statistics, model estimates, and p-values. **Figures** (e.g., bar charts, box plots, scatter plots) will illustrate data distributions, group comparisons, and model diagnostics.

Confidence Intervals (95%) will accompany key estimates to indicate precision. **Text** will highlight main findings, including any deviations or unexpected results. These methods will ensure clarity and support interpretation of the study's outcomes.

• Interpretation of Results:

Significant findings (p < 0.05) will be interpreted as evidence of an association or effect, while non-significant findings will not be taken as proof of no effect but rather as inconclusive. Effect sizes and confidence intervals will be emphasized to assess clinical relevance, regardless of statistical significance.

• Potential limitations of the Analysis:

This is a pan European study including patients from 24 sleep centers in 15 countries. New technology will be applied to all patients and health care professionals. The following limitations of the analysis may occur:

- Heterogeneity Across Centers: Differences in referral patterns, clinical routines, experience with remote technology, and treatment traditions across the 24 centers in 15 countries may introduce variability that is not fully accounted for, potentially affecting the comparability of patient populations and treatment effects.
- **Health System Variability**: Diverse healthcare infrastructures and access to care may influence treatment delivery, follow-up, and adherence, impacting outcome measures.
- Cultural and Societal Influences: Variations in cultural attitudes toward symptoms, treatment expectations, and doctor-patient interactions may affect both patient-reported outcomes and clinician assessments.
- **Baseline Differences**: Systematic differences in symptom burden and patient expectations at baseline between countries or centers may confound treatment effects, even after statistical adjustment.

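### Section 8.4 carries no non-inferiority criterion: its 95% CI and unspecified p-values match neither the 30-minute margin nor the one-sided 1% level that Section 6 used to size the trial

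*SAP*

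**What the plan says.** Section 6 (Sample Size Calculation) fixes the design: "We decided to use a non-inferiority study design with 30 minutes as a threshold for equality of staff time". Its power table uses alpha 1%, power 90%, SD 120 minutes and a limit of 30 minutes. The accompanying calculator text expresses success through the "lower limit of a one- sided 99% confidence interval (or equivalently a 98% two-sided" interval, which must lie above -30. The planning assumption is that SR and standard care take equal time.

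Section 8.4 (Primary Analysis) again labels the comparison as non-inferiority. It fits a mixed model with a fixed group effect, beta1, and a random centre effect. Its inference paragraph reads: "The estimated mean difference in staff time between groups will be reported with 95% confidence intervals and p-values". The 30-minute limit, the 1% level, a null value and a rule for success do not appear there. The groups are called A and B and are not matched to SR and SC.

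Section 13 (Reporting and Interpretation of Results) gives the general reading rule: "Significant findings (p < 0.05) will be interpreted as evidence of an association or effect". Non-significant results are to be treated as inconclusive. It also sets 95% intervals for key estimates. The primary endpoint is not excepted from either convention.

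**The concern.** A non-inferiority conclusion needs four things fixed in advance: the contrast and its sign, the margin, the confidence level, and the limit that must clear the margin. Section 6 has a version of the last three, but as sample-size output with no stated contrast. Section 8.4, which an analyst will follow, has none of the four and prescribes a different confidence level.

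Two consequences follow. An analyst who applies Sections 8.4 and 13 as written has a significance rule that does not answer the non-inferiority question. An analyst who compares the 95% CI with 30 minutes works at a looser level than the one that produced the sample size. In either case part of the primary decision rule would be chosen at analysis, in an open-label trial.

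**Working it through.** **Inputs**, all from Section 6: one-sided alpha 1%, power 90%, SD 120 minutes, margin d = 30 minutes, assumed true difference 0. Allocation is 1:1 (Section 7). As in the SAP's own calculation, centre variance is ignored.

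**1. Reproduce the sample size.** The SAP's formula is n = (z(1-alpha) + z(1-beta))² × 2 × SD² / d².

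- (2.326 + 1.282)² = 13.017
- 2 × 120² / 30² = 32
- 13.017 × 32 = 416.5, so 417 per group and 834 in total, as stated

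At 90% power, one-sided 0.5% would give 477, one-sided 2.5% would give 337 and one-sided 5% would give 275. The stated figure therefore belongs to one-sided 1%, that is, a two-sided 98% CI.

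**2. Planned precision.** SE = 120 × √(2/417) = 8.31 minutes.

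**3. The two intervals read against the 30-minute margin**, with the difference taken as SR minus SC:

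| | 98% CI (Section 6) | 95% CI (Section 8.4) |
|---|---|---|
| Multiplier | 2.326 | 1.960 |
| Half-width, minutes | 19.3 | 16.3 |
| Largest observed difference that passes, minutes | 30 - 19.3 = 10.7 | 30 - 16.3 = 13.7 |
| Power at true difference 0 | 90.0% | 95.1% |
| False-claim rate at true difference 30 | 1.0% | 2.5% |

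An observed SR minus SC difference between 10.7 and 13.7 minutes passes under one section's level and fails under the other's.

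**4. The Section 13 rule, if the p-value tests beta1 = 0.**

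- At a true difference of 0, p < 0.05 occurs in 5% of trials, so 95% are labelled inconclusive.
- The 98% CI shows non-inferiority when the observed difference is below 10.7. The p-value is 0.05 or more when it lies between -16.3 and +16.3. Both hold between -16.3 and 10.7, with probability 0.900 - 0.025 = 0.875.
- So in 87.5% of trials the design criterion would be met while Section 13 returns inconclusive.

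**5. Direction.** Less staff time is better. A lower limit above -30 is the right criterion for SC minus SR. For SR minus SC the equivalent is an upper limit below +30. Section 8.4 does not say which difference beta1 is.

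**The case against.** The non-inferiority intent is not hidden. Section 8.4 states it, the staff-time procedure in Appendix A repeats it, and Section 6 contains a margin, a level and a CI criterion. Section 13 also says that effect sizes and intervals will be emphasised whatever the significance. A 95% CI can be compared with 30 minutes, so the planned output could support a verdict. All of this stands. The fault is a rule that was not carried into the analysis section, together with conflicting confidence levels. The planned output is not useless.

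A reader might infer more than the SAP supports:

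- **That Section 8.4 prescribes a test against zero.** It names no null. Zero is inferred from the usual test of a model coefficient and from Section 13's rule, so the 95% and 87.5% figures depend on that inference.
- **That the direction in Section 6 is wrong.** It is undefined. The calculator text is correct if the difference is SC minus SR, and nothing in the SAP excludes that.
- **That a small excess inside the margin would be declared an effect although non-inferiority is shown.** At the planned SE of 8.31, p < 0.05 needs an observed excess above 16.3 minutes. Such a result already fails non-inferiority under both intervals (limits 10.7 and 13.7).
- **That the false-claim rate is 2.5 times the planned one.** This holds only if the 95% CI is compared with 30 minutes, which Section 8.4 does not say.

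**Conclusion.** The point holds. Section 8.4 does not state how the primary hypothesis will be decided, and the level it prescribes conflicts with the level behind the 417 per group. The size depends on the reading. If the test is against zero, about 95% of trials with no true difference would be called inconclusive, against a planned 90% chance of showing non-inferiority. If the 95% CI is compared with the margin, the one-sided error is 2.5% instead of 1% and the cut-off moves by 3 minutes, from 10.7 to 13.7. The figures assume 417 analysed per arm, SD 120 and no centre variance. The mismatch of levels and the missing criterion do not depend on those assumptions. This should be corrected before staff time is analysed by group.

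**What to change.** Three changes of wording, made through the amendment procedure in Section 14:

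1. In Section 8.4, define beta1 as SR minus SC, with SC as the reference. State that non-inferiority is concluded if the upper limit of the two-sided 98% CI for beta1 is below +30 minutes. Any p-value for the primary comparison should be computed against the 30-minute null (H0: beta1 ≥ 30).
2. In Section 6, restate the criterion in the same direction, so that both sections give one rule.
3. In Section 13, exempt the primary endpoint from the p < 0.05 reading rule and from the 95% convention for its decision. A 95% CI may still be shown as description.

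The sample size and data collection do not change. The cost is an interval about 19% wider than the 95% CI (2.326 / 1.960 = 1.19), which is the precision that the sample size was calculated for.

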8.5. Secondary Analysis

A number of secondary analyses are listed in chapter 4 and in appendix C, secondary, tertiary and exploratory endpoints. A detailed description of all these analyses to be performed in the upcoming years is not feasible for this SAP. Therefore, only a few most important analyses are described below exemplifying the advanced statistical models to be applied to the large amount of study data.

• Example 1: Association between Overnight Hypoxic Burden and Change in ESS Score

This section describes the analysis plan for evaluating the association between overnight hypoxic burden and the change in ESS score after 3 months of CPAP treatment in the Sleep Revolution study arm, compared to the association between AHI (single night assessment) and ESS change in the conventional management arm. Both models will be adjusted for confounders of ESS change like age, sex, BMI, AHI and ESS score at baseline.

Analysis Population: The primary analysis will be conducted on the intention-to-treat (ITT) population, including all randomized patients according to their assigned group.

Descriptive Statistics: Descriptive statistics will be presented for the primary outcome by group, including: Mean, standard deviation, Median, interquartile range and Minimum/Maximum

Primary Analysis: To evaluate the association between overnight hypoxic burden and change in ESS score, and compare it with the association between AHI and ESS change, two linear mixed-effects models (LMM) will be used:

1. Sleep Revolution Study Arm:

- Fixed effects: Overnight hypoxic burden, age, sex, BMI, baseline AHI and ESS. We will analyse the collinearity between AHI and hypoxic burden metrics. If the collinearity is very high we need to decide to use AHI or HB or we will perform an analysis by tertiles of AHI.

- Random effect: Center

2. Conventional Management Arm:

- Fixed effects: AHI, age, sex, BMI, baseline AHI and ESS

- Random effect: Center

Model specification for the Sleep Revolution and standard care study arm, respectively: ESS_Change_ij = $\beta 0 + \beta 1 *$ HypoxicBurden_ij + $\beta 2 *$ Age_ij + $\beta 3 *$ BMI_ij + $\beta 4 *$ SEX_ij + $\beta 5 *$ BaselineAHI_ij + $\beta 6 *$ BaselineESS_ij + u_j + ϵ_i j where:

- ESS_Change_ij is the change in ESS score for patient i in center j
- β 0 is the intercept
- β 1- β 6 are the fixed effect coefficients
- u_j ~ N(0, σ_u^2) is the random effect for center
- $\varepsilon_{ij} \sim N(0, \sigma^2)$ is the residual error

Estimates and Inference: The estimated associations between hypoxic burden and ESS change, and between AHI and ESS change, will be reported with 95% confidence intervals and p-values. Model assumptions (normality of residuals, homoscedasticity) will be checked using diagnostic plots.

Sensitivity Analyses: Sensitivity analyses will be conducted to assess the robustness of the primary analysis:

- A per-protocol analysis will be conducted.

- If the distribution of ESS change is highly skewed, a log-transformation or non-parametric methods may be considered.

• Example 2: The above-mentioned analysis principle will apply even to the following association analyses:

Association between other predictive capacity of novel sleep apnea severity markers (mean of 3 sleep tests) from the SR pathway compared with traditional OSA severity makers (single night assessment, AHI, ODI, mean SaO2) and the for changes in ESS symptom score, and other secondary diagnostic markers (including the ESQ) variables, and the initial help request after 3 months of CPAP treatment in the sleep revolution study arm compared with the association between traditional OSA severity makers (single night assessment) and the change in ESS after CPAP treatment in the conventional management arm (both models adjusted for confounders of ESS change)

Strongest baseline variable – single or combined parameter - (anthropometrics, comorbidity, novel and traditional sleep apnea severity markers, baseline symptom burden assessed by traditional questionnaires or the European Sleep Questionnaire) as a predictor of improved symptoms improvement and quality of life change in the patient global impression scale (much and very much improved) after 3 months of CPAP therapy

- \circ $\,$ Content validity of the European Sleep Questionnaire
- o Statistical models or tests
- Correction for multiple comparisons (e.g., Bonferroni, Holm)
- Example 3: Safety analysis

All reported AEs will be listed and compared in the two study groups. The incidence of PAP treatment-emergent AEs will be included in incidence tables. Events with missing onset dates will be included as treatment emergent. If a patient experiences more than 1 occurrence of the same AE, the occurrence with the greatest severity and the closest association with the study treatment will be used in the summary tables. SAEs and AEs causing discontinuation will be tabulated. All AEs will be listed by patient, along with information regarding onset, duration, relationship and severity to study treatment, action taken with study treatment, treatment of event, and outcome.

- Vital signs like blood pressure and heart rate will be summarized using descriptive statistics, including mean values and mean change from baseline values, as well as numbers of patients with values outside limits of the normal range at each time point.
- Summary tables will be provided for concomitant medications initiated during the study period.

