- Secondary objective: To evaluate novel Sleep Revolution diagnostic variables and their relation to symptom burden, patient 's help request during baseline assessment and outcome of sleep apnea treatment with CPAP after 3 months.
- Further secondary objectives: Feasibility and safety of the self-applied sleep testing and the digital platform for both sleep and symptom assessment

Study Design:

The study is performed at 24 sites of the European Sleep Apnea Database (ESADA) network in 15 European countries. Most relevant details of the study design are listed below:

- Study SR-001 is a multi-center, 2-arm, cross-over study comparing the diagnostic impact and accuracy of two different diagnostic pathways on the outcome of diagnosis and CPAP treatment in patients with suspected OSA. Patients referred to one of 24 sleep centers of the ESADA network participating in the Sleep Revolution project will be studied using both the clinical routine of OSA evaluation (standard care) and the novel Sleep Revolution based diagnostic pathway including self-applied polysomnography over three nights, digitally based symptom evaluation, and actigraphy based assessment of sleep wake rhythm and physical activity (experimental condition). Study participants will be randomized with respect to the order of two diagnostic pathways. The decision on diagnosis and treatment will be based on information from the first diagnostic procedure (SC or SR), the results from the second pathway will be blinded both to the investigator (sleep specialist) and the patient.
- Following diagnostic steps including sleep testing, symptom assessment and evaluation of physical status evaluation, patients will receive information regarding the sleep disorder diagnosis by the sleep specialist. In case of a diagnosis of clinically relevant OSA, treatment recommendations will be provided. Only patients initiating therapy with PAP will be approached for participation in the subsequent part of the study- treatment start and follow up for 3 months.

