 - Epworth Sleepiness Scale, Insomnia Severity Index, Fatigue Severity Scale, Pittsburgh Sleep Quality Inventory, Depression Anxiety Stress Scale – short version with 21 questions (DASS21), Clinical Global Impression Scales

Capacity of the novel SR diagnostic pathway to detect clinically significant sleep apnea

Sleep apnea severity and sleep quality

SR procedure: 3 nights: Means, Minimum, and Maximum for: AHI, ODI, T90, Total Sleep Time, % sleep stage distribution, hypoxic burden assessed by ABOSA software

- Standard care procedure: AHI, ODI, T90, Total Sleep Time, % sleep stages, hypoxic burden assessed by ABOSA software
- "First night" and "between night" effects: Differences between nights 1, 2 and 3 in the sleep recording results, in particular night 1 versus 2 or 3. Analysis of variability: %supine position, REM-sleep%, and alcohol intake prior to sleep (dichotomic)
- Frequency of OSA diagnosis in Standard Care versus SR care
- Frequency of no sleep apnea, and "mild to severe" OSA according to the AHI criteria AHI<5, 5-<15, 15-<30 and ≥ 30 events/hour in both arms (SR and SC)
- Frequency of treatment recommendations
- Distribution of recommendation for PAP, OD, surgery, weight reduction, no treatment for the two randomised patient groups: Standard care versus Sleep Revolution based diagnosis
- Frequency of other sleep diagnoses in Standard Care versus SR care
- Frequency of insomnia, combined OSA and insomnia (COMISA), Periodic Limb Movement Disorders (PLMD), Restless Legs Syndrome (RLS)

Prespecified subgroup analyses:

- Sex, even pre-post menopause
- Technical feasibility analysis: Age stratification by tertiles
- Weight change group in the PAP follow-up study

Clinically meaningful outcomes of CPAP treatment in patients with OSA

• Adherence with and efficacy of PAP treatment

Mean values for the treatment period, variability of PAP use over time, residual AHI, leakage.

CPAP-non users: Identification of those patient characteristic: more complex analysis of predictors for PAP non -users by parameters from the diagnostic process (standard care and SR case)

• Effects of PAP treatment

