 Results from the European Sleep Questionnaire Change in daytime and nocturnal symptoms assessed by the ESQ at baseline and after 12 weeks of CPAP Association ESQ parameters and PSG variables 	 Clinical variables and daytime and nocturnal symptoms associated with response to CPAP treatment Patient/Clinical Global Impression Scale Improvement (PGI-I/ CGI-I): Percentage of patients reported as improved (scores 1 to 3) from baseline to Week 12
 Patient/Clinical Global Impression Scale Severity (PGI-S/CGI-S): Change in mean score from baseline to Week 12 	 Epworth Sleepiness Scale (ESS): Change in mean total score from baseline to Week 12 Insomnia Severity Index (ISI): Change in mean total score from baseline to Week 12
 Pittsburgh Sleep Quality Index (PSQI): Change in mean global score and in mean scores of domains from baseline to Week 1 Association between PSQI measures and sleep test results from SC and SR care Physical activity and mean sleep duration pre and post CPAP 	Association between overnight hypoxic burden (mean of 3 sleep tests) and the change in ESS score after 3 months of CPAP treatment in the SR study arm compared with the association between AHI (single night assessment) and the change in ESS after CPAP treatment in the conventional management arm (both models adjusted for confounders of ESS change

5. Aims and Hypotheses

Aims

- Analyse differences in staff time associated with the SR pathway compared to Standard Care (SC)
- Apply several novel diagnostic parameters and principles which influence the predictive value of the diagnostic method for CPAP treatment efficacy, tolerance and acceptance.
- Assess the technical feasibility of the novel SR diagnostic pathway including selfapplied polysomnography, and the cloud based digital platform for data transfer and data exchange between patients and caregivers.
- Assess the content validity and the predictive capacity for CPAP success of the newly designed European Sleep Questionnaire (ESQ).

Primary Hypothesis:

• The SR procedure provides more reliable and individualized health data during the diagnostic process compared with standard care without an excess of staff time.

List of secondary Hypotheses:

- The ESQ is able to detect treatable traits in sleep apnea patients not yet captured in standard care questionnaires.
- Novel biomarkers from sleep obtained by continuous and automated analysis provide information which better predicts patient outcome

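### Section 8.5, Example 1: the standard-care model lists AHI twice and disagrees with its own equation, the named population does not fit the outcome, and the comparison cannot attribute a difference to the marker

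*SAP*

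**What the plan says.** Example 1 in SAP section 8.5 plans two linear mixed models for ESS change after 3 months of CPAP, one per randomised arm, each with a random centre effect.

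- **Adjustment set.** "Both models will be adjusted for confounders of ESS change like age, sex, BMI, AHI and ESS score at baseline".
- **Sleep Revolution (SR) arm.** The marker is hypoxic burden, with baseline AHI among the covariates. If collinearity between the two proves very high, one is to be chosen or AHI tertiles used. No threshold is given.
- **Standard-care (SC) arm.** "Fixed effects: AHI, age, sex, BMI, baseline AHI and ESS". The contrast is described as "compared to the association between AHI (single night assessment) and ESS change in the conventional management arm".
- **Equation.** A single equation follows, introduced as "Model specification for the Sleep Revolution and standard care study arm, respectively". Its first slope is for hypoxic burden and its fifth for baseline AHI.
- **Nights.** The endpoint table in section 4 defines the SR side as "Association between overnight hypoxic burden (mean of 3 sleep tests) and the change in ESS score after 3 months of CPAP treatment".
- **Population.** "The primary analysis will be conducted on the intention-to-treat (ITT) population, including all randomized patients according to their assigned group". Section 3 (Study Design) says "Only patients initiating therapy with PAP will be approached for participation in the subsequent part of the study". Section 8.1 places secondary outcomes in the per-protocol cohort, and section 8.3 says the ITT set serves the staff-time analysis.
- **Reporting.** Each association gets its own 95% confidence interval and p-value. No measure is named for comparing the two.

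**The concern.** Three things do not fit together.

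First, the SC marker is the diagnostic single-night AHI, which is a baseline value, and baseline AHI is then listed again as a covariate. The equation does not settle the matter, because it has no separate AHI marker term and includes hypoxic burden, which the SC list omits.

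Second, the outcome exists only for patients who start CPAP and are followed, whereas the named population is everyone randomised.

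Third, marker, number of nights, adjustment set and patients all change at once between the two models. The two coefficients are also in different units.

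At stake is the secondary hypothesis in section 5 that novel sleep biomarkers predict outcome better. As specified, a difference between the two associations could come from the marker, the averaging, the adjustment or the patients, and the analyst would have to choose the SC model and the analysis set after the data are in.

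**Working it through.** The SAP gives no sample size or effect size for Example 1, so there is no stated figure to reproduce. The check compares the passages and works out the size of the distortions under stated assumptions.

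**1. Model terms side by side (section 8.5)**

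| Term | SR list | SC list | Equation for both arms |
|---|---|---|---|
| Hypoxic burden | yes | no | yes |
| AHI as marker | no | yes | no |
| Baseline AHI | yes | yes | yes |
| Age, sex, BMI, baseline ESS | yes | yes | yes |

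The equation agrees with the SR list only. Putting AHI in place of hypoxic burden, to obtain an SC version, would enter AHI twice.

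**2. Identification**

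The SC list plus an intercept gives 7 columns. With both AHI terms equal, the design matrix has rank 6 (checked on 500 simulated patients). With one AHI term it has 6 columns and rank 6.

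If two different AHI measurements were meant, which the SAP does not say, the pairwise variance inflation is 1/(1 − r²). For assumed r = 0.80, 0.90, 0.95 and 0.99 this is 2.8, 5.3, 10.3 and 50.

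**3. Population**

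Section 6 plans 500 patients per group. PAP uptake is not given; assume 30% to 70%. Then 500 × 0.30 = 150 to 500 × 0.70 = 350 per group could have the outcome, and 70% to 30% of the ITT set could not, before any loss to follow-up.

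The per-protocol set in section 8.3 is defined by completing the diagnostic pathway, so it does not pick out PAP starters with a 3-month ESS either.

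**4. Effect of averaging nights, unadjusted**

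Assume single-night reliability R1 = 0.7 (range 0.6 to 0.8; not in the SAP).

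- Three-night reliability: R3 = 3R1/(1 + 2R1) = 2.1/2.4 = 0.875 (0.818 to 0.923).
- For two equally informative markers, the ratio of observed correlations, 3-night to 1-night, is √(R3/R1) = √(0.875/0.7) = 1.12. It is 1.17 at R1 = 0.6 and 1.07 at R1 = 0.8.

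**5. Effect of adjusting hypoxic burden for AHI**

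Assume also a true correlation of 0.8 between the markers, measurement errors independent between them, equal true correlation ρ with ESS change, and no other covariates.

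- *AHI in the SR model also a 3-night mean.* Observed marker correlation: 0.8 × 0.875 = 0.70. Standardised hypoxic-burden coefficient: ρ√0.875/(1 + 0.70) = 0.550ρ. SC coefficient for AHI, entered once: ρ√0.7 = 0.837ρ. Ratio: 0.550/0.837 = 0.66 (0.71 at R1 = 0.6, 0.62 at R1 = 0.8).
- *AHI in the SR model a single night.* Observed marker correlation: 0.8 × √(0.875 × 0.7) = 0.626. Coefficient: ρ(0.935 − 0.626 × 0.837)/(1 − 0.626²) = 0.677ρ. Ratio: 0.677/0.837 = 0.81 (0.89 at R1 = 0.6, 0.73 at R1 = 0.8).
- *Break-even, 3-night AHI.* The two effects cancel when 1 + 0.875c = 1.118, that is, at a true marker correlation c of about 0.13.

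Steps 4 and 5 pull in opposite directions, and the SAP does not say which AHI enters the SR model.

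**The case against.** The strongest reply has four parts.

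**The duplicate term is harmless.** A reader might infer that the SC model cannot be fitted. The documents do not support that. An exact duplicate leaves the fitted values unchanged, only the split between the two AHI coefficients is arbitrary, and section 11 allows predictors with high variance inflation to be removed or combined. Read literally for both arms, the equation has one AHI term and tests AHI net of hypoxic burden. This part stands, and it narrows the point to two conflicting statements of the SC model that must be reconciled.

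**The plan is not shown to favour hypoxic burden.** A reader might take the 1.12 ratio as a built-in advantage. It is an unadjusted figure, and the planned SR model adjusts for AHI, which works against hypoxic burden. The three-night value is also less attenuated rather than inflated. This stands.

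**The contrast is a pathway question.** Three nights belong to the SR pathway, so comparing its marker with the single-night marker of routine care is the declared aim. This stands only in part. A pathway contrast is legitimate, but this model adjusts one marker for the other and names no metric for two associations in different units.

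**Nobody plans to impute ESS for untreated patients.** Section 8.10 permits imputation in general, and a reader might infer that it would be used here. No section says so, and Example 1 itself defines the outcome as after CPAP. This stands, but the ITT sentence is then wrong for the outcome, and it conflicts with sections 8.1 and 8.3.

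Section 8.5 offers these analyses as examples, but also describes them as among the most important.

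**Conclusion.** Wrong as written, on three counts.

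- The SC fixed-effects list and the printed equation contradict each other, and the list leaves the two AHI coefficients unidentified.
- The ITT population does not fit an outcome that only PAP starters can have. The per-protocol set does not identify the right patients either.
- The comparison cannot attribute a difference to the marker, because nights, adjustment and patients differ as well and no comparison metric is given.

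The first two follow from the text alone. So does the third, but the size of its distortion rests on assumptions outside the SAP. At a single-night reliability of 0.7, averaging alone gives a correlation ratio of about 1.12, while adjustment for AHI at a true marker correlation of 0.8 brings the coefficient ratio to 0.66 or 0.81. The net direction is therefore unknown, and no claim of bias towards either marker is supported. The primary endpoint is not affected. The correction should be made before this analysis is run.

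**What to change.** 1. Keep one AHI term in the SC model and print one equation per model.
2. Define the population as PAP starters with baseline and 3-month ESS, and remove the ITT wording from Example 1.
3. Compare the markers in the same patients, both randomised groups together. Section 3 schedules both pathways for every patient. Section 4 lists both markers for the SR procedure and for standard care: "Standard care procedure: AHI, ODI, T90, Total Sleep Time, % sleep stages, hypoxic burden assessed by ABOSA software".
4. Use a common base model with age, sex, BMI, baseline ESS, randomised group and centre. Add AHI and hypoxic burden in turn, like for like: once with both as 3-night SR means, and once with both from the single SC night. Adjust the SC version for polygraphy versus polysomnography, since section 7 fixes the method by centre.
5. Report the bootstrap difference in marginal R-squared with a confidence interval. Adding the markers in turn also removes the need for a collinearity rule without a threshold.
6. If the pathway contrast (3-night SR against single-night SC) is wanted, keep it as a separately labelled analysis.
7. Apply the same changes to Example 2.

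The cost is revised SAP wording and a re-specified model, with no new data. The downside is that patients lacking one of the two tests leave the paired comparison; their number should be reported.
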